**Document History – Changes compared to previous final version of SAP**

Date	Time point	Reason for update	Outcome for update	Section and title impacted (Current)
24-Jun-2015	Prior to DB lock	Creation of initial version	N/A - First version	NA
07-Dec-2016	Prior to DB lock	Since the enrollment in the study was halted after only a few patients treated, short close-out CSR to be produced.	Aligned to Short close-out guideline	
 
• [Protocol Section 10.3.1 Study Treatment]: The actual dose, dose intensity, relative dose intensity and total daily doses of each agent will not be summarized or listed.
 
• [Protocol Section 10.3.2 Concomitant therapies]: Concomitant medications and significant non-drug therapies prior to and after the start of the study drug treatment will not be summarized or listed.
 
• [Protocol Section 10.3.3 Compliance]: The listing of patients with protocol deviations will be provided; no summary tables will be produced.
 
• [Protocol Section 10.4.2] The primary efficacy endpoint, PFS will not be analyzed. Log-rank test, HR estimates and related confidence interval and Kaplan-Meier estimates with confidence interval for median survival and survival probabilities will not be performed.
 
• [Protocol Section 10.5.2 Other secondary efficacy objectives]: BOR, ORR and DCR will not be summarized and corresponding confidence interval will not be produced. Kaplan-Meier plots for DOR will not be produced and the median DOR will not be estimated. Kaplan-Meier estimates for OS with confidence intervals will not be produce and OS rate
 

---

Date	Time point	Reason for update	Outcome for update	Section and title impacted (Current)
				
and related confidence interval will not be performed. Listing of Overall response, time to progression time to onset and duration of overall response will not be provided. Waterfall plot will not be produced.
 

• [Protocol Section 10.5.3 Safety objectives]: Laboratory abnormalities, ECG, Cardiac Imaging and vital signs summary tables and listings will not be provided. Tolerability of the study drug will not be summarized and reason for dose interruption, dose reduction and dose change will not be listed by patient or summarized.

 

---

## **1 Introduction**

[figure not shown]
This document describes the detailed statistical methodology for the Report Analysis Plan (RAP) of study CLEE011X2201 Protocol Amendment 2. The data will be analyzed by Novartis and/or designated CRO. It is planned that the data from all centers that participate in this protocol will be used.

The purpose of the CSR is to report the assessment of clinical efficacy and safety of the LEE011 in patients with relapsed, refractory, incurable teratoma with recent progression.

The list of tables to provide at each analysis will be detailed in Module 7.

All changes to the planned analysis described in Modules 3, 7 and 8 required before or after database lock will be made through an amendment or an addendum, respectively. Note that obvious corrections will be made at the time of analysis to address minor formatting or spelling mistakes present in RAP modules without the need to amend these modules.

## 1.2 Objectives and endpoints

[figure not shown]
The study objectives and corresponding endpoints are shown in [Table 1-1](#).

**Table 1-1 Objectives and related endpoints**

Objective	Endpoint
Primary	
To assess the efficacy of LEE011 compared to placebo in patients with relapsed/refractory teratoma with recent progression	PFS as per RECIST v1.1 (by local investigator assessment).
Secondary	
To assess other measures of efficacy of LEE011 compared with placebo	BOR, ORR, DOR, DCR at 4 months as per RECIST v1.1 and OS, OS Rate at 12 months.
To assess safety and tolerability of LEE011	Incidence and severity of adverse events and serious adverse events, changes in

compared with placebo

laboratory values, electrocardiograms, and vital signs will be used to assess the safety as per CTCAE v.4.03. Dose interruptions and changes will be used to assess the tolerability.

### **1.3 Data Analysis**

Data will be analyzed by Novartis and/or designated CRO according to the data analysis section 10 of the clinical study protocol [CLEE011X2201] and will be available in CSR Appendix 16.1. Important information will be given in the following sections and details are provided as applicable in CSR Appendix 16.1.9.

All statistical analysis will be performed using SAS® version 9.3.

### **1.4 CSR related reporting events**

The following points will guide the production of all or subset of the planned analyses:

- The primary CSR includes all outputs described in Module 7 based on all patients' data at the time when there are approximately 23 PFS events for the primary efficacy analysis and all patients have been followed for PFS for at least 6 months or have discontinued prior to this time for disease progression or death, or have withdrawn consent to follow up or have been lost to follow up or if the study is terminated early [Protocol CLEE011X2201 Section 4.4].
- If there will be additional data for patients continuing on study or in survival follow-up past the data cutoff date for the primary CSR, they will be reported in a final CSR once the

treatment period, safety follow-up, disease progression follow-up and survival follow-up periods have ended for all patients as described in [Protocol CLEE011X2201 Section 7.1.4]. The content of the final CSR is determined based on instructions outlined in [OTM Guidelines for Patients that Continue Beyond Study Data Cutoff].

## **2 Definitions and general methodology**

### **2.1 General definitions**

#### **2.1.1 Study drug**

**Study drug** is defined as LEE011 or matching placebo.

**Study treatment** is defined as LEE011 or matching placebo.

#### **2.1.2 Assessment windows, baseline and post baseline definitions, missing data handling**

##### **2.1.2.1 Date of first administration of study drug/ treatment**

The date of first administration of study drug is derived as the first date when a nonzero dose of study drug was administered and recorded on the dose administration DAR eCRF. The date of first administration of study drug will also be referred as *start of study drug*.

##### **2.1.2.2 Date of last administration of study drug/ treatment**

The date of last administration of study drug is defined as the last date when a nonzero dose was administered and recorded on DAR (e)CRF.

##### **2.1.2.3 Study drug exposure**

The following algorithm will be used to calculate the duration of study drug exposure (in cycles and in days) for patients takes at least 1 dose of the study drug:

Duration of exposure (days) = last date of exposure to study drug – date of first administration of the study drug + 1

For patients who did not take any drug, the duration of exposure is defined as zero.

##### **2.1.2.4 Study day**

The study day, describes the day of the event or assessment date, relative to the reference start date (randomization date).

The study day for safety assessments (e.g. adverse event onset, laboratory abnormality occurrence, vital sign measurement, dose interruption etc.) will be calculated as the difference between the date of the assessment and the start of study treatment plus 1. (Note: if an adverse event starts before the start of study treatment the study day displayed on the listing will be negative and will be calculated as the difference between the date of the assessment and the start of study treatment.).

The study day for all other non-safety assessments (i.e., tumor assessment, death, disease progression, tumor response, ECOG performance status, [REDACTED]) is defined as the difference between the date of the event and the randomization date plus 1. In other words, all efficacy time-to-event variables (e.g. progression-free survival, overall survival, time to response) will be calculated from date of randomization. (Example: if randomization date is 15DEC2013, start of study drug is on 18DEC2013, and the date of death is 28DEC2013 then the study day when the death occurred is 14).

The study day will be displayed in data listings.

Study day is not to be used in numerical computations, for example in calculating exposure.

### **Cycle definition**

The study day for all assessments is calculated using the randomization date as Day 1.

The cycle number and day within cycle attributed to a visits or assessment will be derived according to the following rules:

- C1D1 (cycle 1 day 1) coincides with the start date of drug/treatment
- All pre-treatment assessments are displayed as **Cycle 0** with a negative day (e.g., **Day -1** for the day before the patient started treatment) or with day 1.
- Day 1 of a cycle corresponds to the day reported by investigator on the start of cycle log form.
- For all cycles but the last, the end date of a cycle is defined as the day before Day 1 of the following cycle as recorded on the cycle log form.
- The end date of the last cycle is when treatment administration is permanently discontinued at the latest of the following days:
  - Date of last administration
  - 28 days after the first day of the last cycle or day of patient's death if earlier when date of last administration is not known
- All post-cycles assessments are displayed as follow-up and with, by analogy, Day 1 representing the first day after the end of the last cycle.

The duration (in days) of a cycle is defined as the cycle end date – cycle start date + 1.

Cycle number and day within cycle are computed to be displayed in listings only.

#### **2.1.2.5 Baseline**

Baseline is considered as the last available assessment performed or value measured within 28 days before the first administration of study treatment, unless otherwise stated under the related assessment section. Baseline could be the day before first treatment administration or the same day as first treatment administration if a pre-dose assessment/value is available (e.g., ECG, [REDACTED]).

If time is recorded for the first treatment dose and for a specific assessment performed the day of first dose, this assessment will be considered as baseline only if it is actually performed before the first dose, as checked using both times.

For those patients eligible to crossover to LEE011 treatment after initial progression, baseline will be adjusted to the last assessment prior to secondary treatment phase. Re-baseline could be the day before first treatment after crossover administration or the same day as first treatment administration after crossover if a pre-dose assessment/ value is available.

If time is not recorded, a specific assessment performed the day of first dose administration will be considered as baseline if, according to protocol, it should be performed before the first dose.

If patients have no value as defined above, the baseline results will be set to missing.

### **2.1.2.6 On-treatment assessment/event**

Safety summaries and selected summaries of deaths will summarize only on-treatment assessments/events. On-treatment assessment/event is defined as any assessment/event obtained in the time interval:

Date of first administration of study treatment through the date of last administration of study treatment + 30 days, i.e. including the lower and upper limits. (Note: However, the calculation of study treatment duration may use different rules as specified in [Section 3.3.1.1.](#))

Adverse events that begin or worsen after informed consent should be recorded in the Adverse Events CRF. Conditions that were already present at the time of informed consent should be recorded in the Medical History page of the patient's CRF.

If the last date of study treatment is missing, on-treatment assessments/events include any assessment/event recorded in the database and which occur after the start date of study treatment.

Data listings will include all assessments/events, flagging those which are not on-treatment assessments/events.

Note: The date of first administration of study treatment in the randomized treatment phase and the date of last administration of study treatment in the randomized treatment phase are defined in [sections 2.1.3.1](#) and [2.1.3.2](#), respectively.

For patients who crossed over to LEE011, the placebo group will include all events before the date of first administration of LEE011 and will not include the 30 days are described above. While the LEE011 crossed over group will include all events after the date of first administration of LEE011 and will include the 30 days.

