6.1.4 Treatment duration

Efficacy, safety and survival data will continue to be collected as per visit schedule (Table 7-1). Patients may continue treatment with study drug until disease progression as assessed by RECIST v1.1 (Appendix 1), occurrence of unacceptable toxicity that precludes any further treatment, or if treatment is discontinued at the discretion of the investigator or by patient's withdrawal of consent. Patients who progress on placebo may crossover to LEE011 and receive treatment until subsequent tumor progression, discontinuation at the discretion of the investigator or patient's withdrawal of consent (see Section 4.1.6). Patients receiving LEE011 may be allowed to continue treatment following progression if in the opinion of the investigator they are receiving clinical benefit. Details supporting continuation must be sent to Novartis for approval within 7 days of documented progression. For patients continuing on LEE011 after unblinding due to clinical benefit (not crossover patients), subsequent tumor assessments should be conducted according to local practice.

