7.1.2 Treatment period

During the treatment period, the patient must follow the Investigator's instructions with regards to contraception, concomitant medications, and dosing regimen (see [Section 6.1.1](#)). There is no fixed treatment duration. Patients may continue study drug until disease progression, unacceptable toxicity, discretion of the investigator or patient withdrawal of

consent. At time of documented progression per RECIST v1.1, patients may be unblinded and those randomized to placebo will be evaluated for crossover to LEE011. Patients should receive LEE011 within 28 days of the last radiological assessment. Safety labs and assessment are not required to be repeated for patients who start crossover C1D1 within 14 days of completing treatment. Patients initially randomized to the LEE011 arm may be permitted to continue on LEE011, despite progression, if the investigator documents ongoing clinical benefit for the patient in the source documentation, in a comment in the eCRF, and discussed decision with CPL. Please refer to [Section 4.1.6](#).

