All data collected during the optional crossover to LEE011 from placebo will be listed separately. This data will be summarized within the planned analyses. The data will not be pooled with the data from patients receiving LEE011 from the outset of the study unless otherwise specified below. Data collected after progression on LEE011 (in the situation which a patient continues to receive the study drug due to clinical benefit) will be listed but will not be pooled in analyses with data collected prior to disease progression.

Further details of statistical analysis and reporting will be described in the RAP.

For screen failure patients the eCRF data collected ([Section 7.1.1.2](#)) will not be included in any analysis but will be reported in the CSR as separate listings.

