## 3 Statistical methods used in reporting

Data will be summarized with respect to demographic and baseline characteristics, and safety observations using descriptive statistics (quantitative data) and contingency tables (qualitative data). They will be reported using FAS.

Categorical data will be presented as frequencies and percentages. For continuous data, mean, standard deviation, median, 25th and 75th percentiles, minimum and maximum will be presented.

Listing will be reported separately for:

- (a) Patients randomized in placebo arm, until they stop to switch to LEE011 or discontinued the study, whichever occurs first
- (b) Patients randomized in LEE011 arm
- (c) Patients who crossover to LEE011 arm from the time of first LEE011 dose

Summary tables will be reported only for patients in (a) and (b) specified above.

Listings of all raw data will be produced and ordered by treatment arm, center, country and patient. Unless otherwise specified, if multiple measurements are available for one time point (or period), an average will be provided to represent the time point (or time period). Unless specified otherwise, all percentage is with respect to big N.

Screen failure patients are those who signed the informed consent, but never started the study treatment for any reason. For these patients, the only information collected on the eCRF is the screening log and the demography pages. These will not be included in any analysis, but will be reported in the CSR as separate listings.

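### No safety window cuts LEE011 data at progression, although Protocol Section 10 bars pooling later LEE011 data with earlier data, and the visible SAP text does not declare the choice

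*SAP*

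**What the plan says.** Continuing LEE011 after progression is a planned pathway. Protocol 6.1.4 states: "Patients receiving LEE011 may be allowed to continue treatment following progression if in the opinion of the investigator they are receiving clinical benefit". Protocol 7.1.2 adds: "At time of documented progression per RECIST v1.1, patients may be unblinded".

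The opening text of Protocol Section 10 sets the rule for the data that follow. Data collected after progression on LEE011, where the patient stays on drug for clinical benefit, "will be listed but will not be pooled in analyses with data collected prior to disease progression".

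The SAP's rules for safety summaries are these:

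- SAP 2.1.2.6 defines the on-treatment interval as "Date of first administration of study treatment through the date of last administration of study treatment + 30 days".
- SAP 2.1.2.2 fixes the end of dosing as "the last date when a nonzero dose was administered and recorded on DAR (e)CRF".
- SAP 3 defines reporting group (b) as "Patients randomized in LEE011 arm", with no time limit, and says "Summary tables will be reported only for patients in (a) and (b) specified above".
- SAP 3.6 closes the safety tables 30 days after treatment discontinuation. Its only special case is the placebo patient who crosses over, whose placebo time ends at the first LEE011 dose.

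Protocol 10.5.3.1 has its own on-treatment period, also from first dose to 30 days after the last dose with no reference to progression. Protocol 10.5.3.2 says that every recorded adverse event will be summarized.

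**The concern.** The Section 10 rule describes exactly the patients who stay on LEE011 after progression, yet no safety window in either document puts it into effect. A programmer working from the SAP would carry such a patient's events to 30 days after the last dose and count them in the LEE011 column.

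This matters because SAP Section 4 drops the PFS, response and survival analyses. The summaries of adverse events, serious adverse events, deaths and events of special interest become the main between-arm output of the close-out report. Time after progression differs from earlier time in two ways: the disease has grown, and the patient may have been unblinded, so relatedness may be judged with the drug known. The placebo column stops at the first LEE011 dose, while the LEE011 column runs past progression. A reader of the table could not tell which period an event came from.

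**Working it through.** The check is mainly a comparison of texts.

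1. **The no-pooling rule.** The preceding sentence in Protocol Section 10, on crossover data, allows exceptions specified later. The sentence on post-progression LEE011 data has no such clause and does not exempt safety.

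2. **The protocol's safety window.** Protocol 10.5.3.1 divides observation into before, during and after treatment by dosing dates alone. Protocol 10.5.3.2 then summarizes all adverse events. Neither mentions the Section 10 rule, so the two parts of the protocol conflict for a patient treated beyond progression.

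3. **The SAP's window and groups.** SAP 2.1.2.6 and 3.6 follow the 10.5.3.1 window. Groups (a) and (c) in SAP 3 are bounded at the crossover, but group (b) is not bounded. A note in 2.1.2.6 mentions the randomized treatment phase, but it points to SAP sections 2.1.3.1 and 2.1.3.2, which do not exist. The matching definitions, 2.1.2.1 and 2.1.2.2, do not stop at progression.

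4. **Declared changes.** The visible text of SAP Section 4 does not mention the pooling rule. Some bullets there are redacted, although the list is introduced as analyses that will not be performed.

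5. **What the window does (assumed dates).** Take first dose on day 1, progression on day 57 and last dose on day 197.
   - End of the SAP window: 197 + 30 = day 227.
   - Time after progression inside the window: 227 − 57 = 170 days.
   - Under the Section 10 rule, events in those 170 days are listed but not pooled with earlier ones.

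6. **Weight of one patient.** Enrollment was 10 (protocol Amendment 3 status; SAP Section 4), randomized 2:1.
   - Expected number on LEE011: 10 × 2/3 = 6.7, about 7. The actual split is not stated.
   - One patient: 1/7 = 14.3%, about 14 percentage points.
   - SAP 3.6.1 counts a patient once per event category, at the worst grade. The shift therefore arises only if the patient had no such event before progression, or if the worst grade changes.

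7. **Number affected.** Neither document gives it. On 18-Aug-2017 four patients were on treatment, three blinded and one crossed over. Protocol 6.1.4 describes continuation for benefit as following unblinding. On that reading none of the four was then a known LEE011 continuer. Earlier or later continuers cannot be excluded, and none is shown.

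**The case against.** The strongest reply is that the SAP does what the protocol's safety section asks. Its window matches Protocol 10.5.3.1, and 10.5.3.2 calls for all adverse events to be summarized. This stands. A reader might infer that the SAP departed from the protocol on its own, or that it contradicts itself because SAP 1.3 says analysis follows Protocol Section 10. Neither is supported, because Section 10 contains both the no-pooling rule and the uncut window. It also means that an edit to the SAP alone would leave a conflict with 10.5.3.1.

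A second reply is that safety tables normally cover all exposure, and these patients are still taking LEE011, so counting their events under LEE011 misattributes nothing. That is a defensible choice. A hard cut at progression has drawbacks: it removes on-drug serious events from the main table, and it denies continuing patients the 30-day tail that patients who stop at progression keep. But Section 10 states a different choice, and nothing visible in the SAP replaces it.

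A third reply is that pooling is inferred from silence, because no SAP sentence says outright that post-progression events are counted. The table list in Module 7 is not available either. This is fair, but the window and group definitions as written admit those events.

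Part of the worry about disease symptoms is also limited by Protocol 8.1.1, which keeps documented progression out of serious adverse event reporting.

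**Conclusion.** The point holds as a reconciliation issue between Protocol Section 10, Protocol 10.5.3.1 and 10.5.3.2, and SAP 2.1.2.6, 3 and 3.6. As written, LEE011 events after progression would be pooled with earlier ones, and the visible text of SAP Section 4 does not declare that.

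The size rests on two unknowns: the number of patients who continued, and the actual allocation. With none, the tables do not change. With about 7 on LEE011, each affected patient could move a given adverse event row by about 14 percentage points.

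Two stronger conclusions are tempting. One is that the LEE011 safety results are in fact distorted; the documents do not show that any patient continued beyond progression. The other is that post-progression data may appear only in listings; Section 10 bars pooling with earlier data but does not bar a separate summary.

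**What to change.** - **Reconcile the texts.** State in Protocol 10.5.3.1 and 10.5.3.2, and in SAP 2.1.2.6, 3 and 3.6, how the Section 10 rule applies to safety.
- **Add a derived flag.** For patients randomized to LEE011 who continue beyond RECIST progression, mark events after documented progression. Progression and dosing dates are already collected.
- **Split the summaries.** Show adverse events, serious adverse events and events of special interest up to documented progression, separately from later events, which are flagged and listed.
- **If an all-exposure table is kept,** declare it in SAP Section 4 as a departure from the Section 10 rule and show the pre-progression table alongside.
- **State the 30-day rule.** Say how the tail is handled for patients who continue, so that they and those who stop at progression are treated in a known way.
- **Leave deaths whole.** Keep the summary of all deaths in SAP 3.6.2 intact, with post-progression deaths flagged.

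The cost is wording, one flag and one table split. The downside is small counts in each part. If no patient continued, a sentence saying so replaces the split.

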7.2.2 Safety and tolerability assessments

Safety and tolerability will be monitored by assessing the changes from baseline in physical exam, vital signs and laboratory measures and by collecting the AEs at every visit. All safety assessments should be performed pre-dose unless otherwise specified. For details on AE collection and reporting, see [Section 8.2](#).

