10.5.3.1 Analysis set and grouping for the analyses

[figure not shown]
For all safety analyses, the Safety Set will be used. All listings and tables will be presented by treatment arm with patients classified according to treatment received.

The overall observation period will be divided into three mutually exclusive segments:

1. pre-treatment period: from day of patient's informed consent to the day before first dose of study drug
2. on-treatment period: from day of first dose of study drug to 30 days after last dose of study drug
3. post-treatment period: starting at day 31 after last dose of study drug.

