### **3.6 Safety evaluation**

The assessment of safety is based on the type of AEs and frequency of AEs as well as on the number of laboratory values that fall outside of pre-determined ranges (Common Toxicity Criteria [CTC] version 4.03 grading limits or normal ranges as appropriate).

The Safety set will be used for summaries and listings of all safety data in Section 14 of the CSR. Safety analyses will be performed per treatment received (see [Section 2.1.1.2](#)). The FAS will be used for Section 16 of the CSR, including for safety listings. These listings will be displayed per intended treatment as per all analyses performed on the FAS (see [Section 2.2](#)). Differences between treatment received and intended treatment, if any, will be provided in a listing.

The safety summary tables will include only assessments collected no later than 30 days after study treatment discontinuation. All safety assessments will be listed, and those collected later than 30 days after study treatment discontinuation will be flagged.

For patients who crossed over to LEE011, the placebo group will include all events before the date of first administration of LEE011 and will not include the 30 days are described above. While the LEE011 crossed over group will include all events after the date of first administration of LEE011 and will include the 30 days.

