### **3.6.3 Laboratory data**

Summary of notable hepatic laboratory values will be produced by treatment. Liver function test values will be listed. No other laboratory data will be analyzed.

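### Under the SAP, a pre-dose liver test on the day of first dose is both the baseline and an on-treatment value, so the notable hepatic summary can count an abnormality that preceded any drug

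*SAP*

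**What the plan says.** **On-treatment.** SAP 2.1.2.6 gives the window as "Date of first administration of study treatment through the date of last administration of study treatment + 30 days", and adds "i.e. including the lower and upper limits". The window decides what enters the tables: "Safety summaries and selected summaries of deaths will summarize only on-treatment assessments/events". Protocol 10.5.3.1 has the same lower limit: "on-treatment period: from day of first dose of study drug to 30 days after last dose of study drug".

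**Baseline.** SAP 2.1.2.5 takes the last available value in the 28 days before first dose. It allows this to fall on the "same day as first treatment administration if a pre-dose assessment/value is available". Where no clock time is recorded, a first-dose-day value still counts as baseline if the protocol plans it before dosing.

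**Timing of the sample.** Protocol 7.2.2: "All safety assessments should be performed pre-dose unless otherwise specified". Protocol Table 7-1 marks chemistry at C1D1, and Table 7-3 places ALT, AST and bilirubin under chemistry. Protocol 7.2.2.5 waives the C1D1 sample when laboratory tests were completed in the preceding 72 hours.

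**The output.** SAP 3.6.3: "Summary of notable hepatic laboratory values will be produced by treatment". SAP 3.6 adds one general limit on safety tables: "The safety summary tables will include only assessments collected no later than 30 days after study treatment discontinuation".

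**The concern.** A value measured before the patient has taken anything should describe the patient's starting state. Here the same record also qualifies as something that happened on LEE011 or placebo. If it is abnormal, the hepatic summary can credit study treatment with a finding that came first.

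The liver is where this matters most. The rationale for Amendment 2 cites a potential risk of hepatic toxicity, and most of the transaminase rules in Protocol Table 6-4 depend on the baseline grade or value. Protocol 10.5.3.3 planned tables that would have shown baseline status: newly occurring grade 3 or 4 toxicities and shifts from baseline. SAP Section 4 drops the laboratory abnormality tables, so that protection is gone while 3.6.3 keeps a hepatic summary that needs it.

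**Working it through.** The documents state no figure to reproduce. The check applies the written rules to dated samples.

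**Rules**
1. Baseline-eligible (SAP 2.1.2.5): taken before first dose and no more than 28 days earlier.
2. On-treatment (SAP 2.1.2.6): first-dose date ≤ sample date ≤ last-dose date + 30 days.
3. On-treatment when the last-dose date is missing (SAP 2.1.2.6): sample date after the start date.
4. On-treatment with the proposed filter: rule 2, and not a baseline or pre-dose record.

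**Hypothetical dates.** First dose 10 March 2015 at 09:00; last dose 1 June 2015. The window under rule 2 runs from 10 March to 1 July 2015.

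| Sample | Baseline-eligible | On-treatment, main rule | On-treatment, last date missing | On-treatment, with filter |
|---|---|---|---|---|
| Day -10, 28 February | yes | no | no | no |
| Day -2, 8 March | yes | no | no | no |
| C1D1 pre-dose, 10 March 08:00 | yes | **yes** | no | no |
| C1D15, 24 March | no | yes | yes | yes |

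Only the C1D1 pre-dose sample has both statuses under the main rule. It also changes status when the last-dose date is missing, so SAP 2.1.2.6 treats the first-dose day in two ways.

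**Does another rule remove it?** SAP 3.6 sets an upper limit only. SAP 3.6.3 has no post-baseline or newly-occurring condition. The SAP's cycle definition labels pre-treatment assessments Cycle 0, including some with day 1, but says cycle and day are for listings only. The Safety Set definition in SAP 2.2 does use the idea of a post-baseline assessment, but it is not carried into 3.6.3.

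**A record that would be misplaced.** Suppose the notable cut-off is ALT above 3 x ULN (assumed). A patient with liver metastases has ALT 4 x ULN pre-dose on C1D1. Protocol 5.3 excludes such patients only from 5 x ULN, and 4 < 5. Every later value is at or below 2 x ULN. On post-baseline values the patient is not notable; as written, the patient is notable on treatment.

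**Size if it happens once.** The documents give 10 patients and a 2:1 ratio but not the actual split. At 7 and 3, one patient is 1/7 = 14 percentage points on LEE011 or 1/3 = 33 on placebo. At 6 and 4 it is 1/6 = 17 or 1/4 = 25. These figures are conditional on one misplaced patient; they are not expected effects.

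**The case against.** The strongest reply is that the path is narrow and part of it lies out of sight.

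- **The SAP follows the protocol.** Protocol 10.5.3.1 starts on-treatment on the same day. That is so, and the convention suits adverse events. The difficulty comes from joining it to a same-day baseline for laboratory values.
- **Notable is undefined in the supplied text.** The SAP refers output details to other modules, which were not supplied. A post-baseline condition in a table shell would close the gap. This stands as a limit on the finding.
- **Few patients can be affected.** Without liver metastases, Protocol 5.3 excludes AST/ALT above 2.5 x ULN, and the protocol summary excludes above 3 x ULN. A pre-dose value past 3 x ULN therefore needs liver metastases or a rise after screening. Patients tested in the prior 72 hours need no C1D1 sample, and their earlier sample falls outside the window. A patient with a later notable value is counted either way. All of this stands, although nothing in the supplied text applies the eligibility limits again to the C1D1 sample.
- **The listing helps.** SAP 3.6.3 lists liver function values, and ten patients can be checked by eye. This reduces the harm but does not correct the table.
- **The table itself is in doubt.** SAP Section 4 says laboratory abnormality summaries and listings will not be provided, while 3.6.3 keeps the hepatic ones. If Section 4 prevails, the consequence disappears.

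A reader might infer that the overlap also distorts baseline-to-worst shift tables and the ECG and vital-sign summaries. The documents do not support that, because SAP Section 4 cancels those outputs.

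**Conclusion.** The overlap is real on the text: a C1D1 pre-dose liver test is both baseline and on-treatment, and nothing supplied keeps it out of the notable hepatic summary. The severity is minor. The effect is confined to one descriptive table in a 10-patient study, and only for a patient who meets all three conditions: a C1D1 sample was drawn, its pre-dose value passes the notable cut-off, and no later value does.

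The conclusion assumes that 3.6.3, not Section 4, governs whether the table is produced, and that no post-baseline condition sits in a module outside the supplied text. The documents give no basis for estimating how many of the ten patients are affected, and it may be none. It would be too much to infer that the trial's liver findings are biased toward LEE011: the same rule applies to both randomised arms, and patients with normal baseline tests are unaffected. No efficacy analysis, type I error or power is involved.

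**What to change.** 1. In SAP 2.1.2.6, keep the date-based window for adverse events. For laboratory assessments, exclude from on-treatment any record selected as baseline under 2.1.2.5, and any first-dose-day record taken pre-dose or planned by the protocol as pre-dose.
2. Apply the same lower limit when the last-dose date is missing.
3. In SAP 3.6.3, state that the notable hepatic summary uses post-baseline on-treatment values, and flag the baseline value in the liver-test listing.
4. In SAP Section 4, record the departure from Protocol 10.5.3.1, and reconcile that section with 3.6.3 on whether the hepatic summary and listing are produced.

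The cost is a few sentences in the SAP and one programming filter. No new data are needed.
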